5.4. Randomization and Blinding

Treatment allocation/randomization for this study will occur centrally through the use of an interactive response technology (IRT). Participants eligible for the study will be randomized in a 1:1:1:1 ratio to receive once daily doses of 10, 20, or 30 mg JZP385 or placebo. Randomization will be stratified by the TETRAS composite outcome score (\leq 17 and > 17), as assessed at the Baseline.

A double-blind approach will be used throughout the 12-week treatment period. During the study (including the titration period), the number of capsules taken each day will be the same for patients randomized to each treatment. JZP385 and placebo capsules will look and feel identical.

The IRT will be programmed with blind-breaking instructions. In case of an emergency, the investigator has the sole responsibility for determining if unblinding of a participants' intervention assignment is warranted. Participant safety must always be the first consideration in making such a determination. If the investigator decides that unblinding is warranted, the

^a The JZP385 DR2 formulation is delayed release formulation 2; details of the formulation can be found in the JZP385 IB.

^b The dose strength of JZP385 is based on the active moiety in the drug product.

investigator should make every effort to contact the sponsor prior to unblinding a participant's intervention assignment unless this could delay emergency treatment of the participant.

If a participant's intervention assignment is unblinded, the sponsor must be notified within 24 hours after breaking the blind. The date and reason that the blind was broken must be recorded in the source documentation and IRT system, as applicable. The participant's treatment assignment may be unblinded for regulatory reporting purposes. Notification of the treatment assignment is only made known to those who require it for safety reporting and submission processes. All other individuals involved in the study, including the investigator, will remain blinded to treatment assignment. Participants for whom the blind is broken for this reason will not be withdrawn from the study.

Sponsor safety staff may unblind the intervention assignment for any participant with an SAE. If the SAE requires that an expedited regulatory report be sent to one or more regulatory agencies, a copy of the report, identifying the participant's intervention assignment, may be sent to investigators in accordance with local regulations and/or sponsor policy.

5.5. Interim Analysis

No interim analysis is planned.

6. ANALYSIS SETS

For purposes of analysis, the following populations are defined:

Table 4Analysis Sets

Analysis Set	Description		
Enrolled	The Enrolled Analysis Set will include all participants who provide informed consent for this study.		
	This set will be used to summarize participants' screening, and inclusion/exclusion from each analysis set as well as reasons for exclusion. Summaries will be presented overall and by the randomization group for those randomized.		
Intent-to-treat (ITT)	The ITT Analysis Set will include all participants who are randomized regardless of taking the study intervention (JZP385 or placebo). This set will be used for standard, baseline characteristics and demographic summaries, as well to be used for efficacy analyses, and participants should be summarized according to the randomized treatment arm.		
Safety	The Safety Analysis Set will include all participants who are randomized and receive at least 1 dose of study intervention (JZP385 or placebo). This set will be used for standard, baseline characteristics and demographic summaries, as well to be used for safety analyses, and participants should be summarized according to actual received treatment arm.		
PK	The PK Analysis Set will include all participants who are randomized and receive at least 1 dose of JZP385 and have at least 1 post-dose evaluable PK concentration. All PK analyses and summaries will be based on the PK Analysis Set.		

7. GENERAL ASPECTS FOR STATISTICAL ANALYSIS

The statistical principles applied in the design and planned analyses of this study are consistent with International Conference on Harmonization (ICH) E9 guidelines (ICH 1998).

7.1. General Methods

In general, results will be summarized by treatment group. Categorical variables will be reported as frequency and percent. Continuous variables will be reported as the number of participants, mean, SD, or SE, median, minimum, and maximum. All summaries, statistical analyses, and individual participant data listings described below will be completed using Version 9.4 or later of the SAS Statistical Analysis System (SAS Institute, Inc. Cary, NC).

7.2. Baseline and Study Day Definitions

7.2.1. Baseline

In general, the Baseline measurement for a variable is defined as the last non-missing value from the baseline visit measured prior to the first dose of the study intervention. If a participant has repeated measurements from the baseline visit, then the last repeated non-missing value will be used. If there is not a value from the scheduled baseline visit, the last non-missing value from other screening or unscheduled visits measured prior to the first dose of study intervention will be used. If a participant who early discontinued without taking the study intervention, the Baseline visit or the latest Screening Visit will be used.

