	SV1	SV2 ^b	Baseline Visit	W1	W2, W3	W4	W5, W6, W7	W8	W9, W10, W11	W12	E/D Visit	EoS Visit / Safety FU ^c	Comments
Days (Window)	-35ª	to -2	-1	7 (-1, +2)	14 (-1, +2); 21±3		35±3; 42±3; 49±3	56± 3	63±3; 70±3; 77±3	84± 3		98 ^d ±3	
Clinic Visit	X	X	X	Xe		Xe		Xe		X	Xe	Xe	
Phone Contact					X ^f		X ^f		X ^f				
Activity													
Urinalysis	X		X	X		X		X		X	X		Repeat urinalysis at the Baseline Visit only if the visit occurs > 35 days after screening.
Blood sample for genetic testing				X									The sample is optional and should be collected at the same time as the predose PK sample.
Supine and standing blood pressure and pulse	х	X	х	x		Х		Х		Х	х	х	SV1, SV2 (if applicable), and Baseline: Triplicate measurements at 15- to 30-minute intervals. All other visits: 1 measurement postdose.
Temperature and respiratory rate	X	X	X	X		X		X		X	X	X	
12-lead ECG	х		Х	Х		х		Х		х	х	х	At each time point, ECGs will be taken in triplicate at approximately 2-minute intervals. Additional ECGs may be obtained at any time per the investigator's judgment.

	1	Scree to 35	ning days ^a)		Doub		nd Treatmen 12 weeks)	ıt Peri	od			Safety Follow-up Period (2 weeks)	
	SV1	SV2 ^b	Baseline Visit	W1	W2, W3	W4	W5, W6, W7	W8	W9, W10, W11	W12	E/D Visit	EoS Visit / Safety FU ^c	Comments
Days (Window)	-35ª	to -2	-1	7 (-1, +2)	14 (-1, +2); 21±3	28±3	35±3; 42±3; 49±3	56± 3	63±3; 70±3; 77±3	84± 3		98 ^d ±3	
Clinic Visit	X	X	X	Xe		Xe		Xe		X	Xe	Xe	
Phone Contact					X ^f		X ^f		X ^f				
Activity													
C-SSRS Screening/ Baseline Version	X												
C-SSRS Since Last Visit Version		X	X	X		X		X		X	X	X	
Instruction on medication washout	X	X											
TETRAS-ADL Subscale	X	X	x			X		X		X	X		At SV1, perform the TETRAS-ADL subscale only for participants who do not need to washout of medications that impact tremor (eg, primidone); otherwise, this assessment should be performed at SV2.
TETRAS-PS	x	X	X			X		X		X	X		The TETRAS-PS will be conducted as indicated in Table 5.
CGI-S	х	X	х			Х		Х		х	x		At SV1, perform the CGI-S only for participants who do not need to washout of medications that impact tremor (eg, primidone); otherwise, this assessment should be performed at SV2.

	I	Scree to 35	ning days ^a)		Doub		nd Treatmen 12 weeks)	ıt Peri	od			Safety Follow-up Period (2 weeks)	
	SV1	SV2 ^b	Baseline Visit	W1	W2, W3	W4	W5, W6, W7	W8	W9, W10, W11	W12	E/D Visit	EoS Visit / Safety FU ^c	
Days (Window)	-35ª	to -2	-1	7 (-1, +2)	14 (-1, +2); 21±3	28±3	35±3; 42±3; 49±3	56± 3	63±3; 70±3; 77±3	84± 3		98 ^d ±3	

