7.2.3. Visit Windows

All scheduled, unscheduled, and early termination assessments will be summarized by derived analysis visit per the Table 5, regardless of whether the visit was performed on-site or remotely. Visit dates will be mapped based on the scheduled Period of each visit, with adjusted analysis-defined visit windows as specified in Table 5.

Table 5 Visit Windows for Assessments or Measurements

Study Period	Scheduled Visit	Scheduled Study Day	TETRAS-ADL, TETRAS-PS, CGIs	CGIc and PGIc	QUEST, SF-36v2, ETEA	C-SSRS ^b , Clinical Laboratory ^{c, e} , Urinalysis ^e , Weight, Vital Signs, Breath Alcohol ^{d, e} , ECG, Urine Pregnancy test
Screening	Visit 1/Visit 2 ^a	-49 to -8	Any Day up to -2	na	n/a	Any Day up to -2
Baseline ^f	Baseline Visit	-1	Closest prior to dosing	na	Closest prior to dosing	Closest prior to dosing
	Week 1	7 (-1, +2)	na	na	na	2 - 14
Double-Blind	Week 4	28±3	2 - 42	2 - 42	na	15 - 42
Treatment	Week 8	56± 3	43 - 70	43 - 70	na	43 - 70
	Week 12	84± 3	71 - 98	71 – 98	2 - max	71 - max
Safety Follow-up	End of Study	98± 3	na	na	2 - max	2 – max ^f

^a Screening Visit 2 is only for participants who need to wash out of any medications that impact tremor (e.g., anti-tremor medications) prior to Baseline;

^b At screening visit 1, C-SSRS screening/baseline version, at screening visit 2, C-SSRS since last visit version;

^c Clinical laboratory includes hematology and chemistry labs;

^dBreath Alcohol is not collected at W1;

^e Not collected at Safety Follow-up.

^f For participants who randomized without taking the study intervention, the Baseline Visit or latest Screening Visit (if Baseline Visit is not available) will be mapped.

If multiple assessments or measurements are recorded within a single visit window (including scheduled, unscheduled, repeated, and retest assessments or measurements as well as early discontinuation data), the following rules will be applied to determine the result from which assessment will be used for the summaries for that analysis visit.

- The priority will always be given to the scheduled visit within the corresponding visit window (e.g., scheduled W4 visit corresponds to Week 4 visit window) regardless of the relative distance to the scheduled Visit Day.
- If there are 2 or more observations within the same visit window, then the non-missing one closest to the scheduled Visit Day will be used in the analysis.

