- If 2 or more observations are equidistant from the scheduled Visit Day, then the non-missing observation with the earliest collection date will be used in the analysis.
- If 2 or more observations are collected on the same day and this day is the closest to the scheduled Visit Day, then the non-missing observation with the earliest collection time will be included in the analysis.

Screening Visit 1 and Visit 2 will be treated as two visits. Observations from the two visits will be summarized separately, as applicable.

If a visit window does not contain any observations, then the data will remain missing for the analysis visit.

Listings will include scheduled, unscheduled, repeated, retest, and early termination data per nominal visits.

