10.4.1. Vital Signs Markedly Abnormal Criteria

Markedly abnormal quantitative vital signs measurements will be identified in accordance with the following predefined markedly abnormal criteria as specified in Table 6.

Table 6 Vital Signs Predefined Markedly Abnormal Criteria

Variable (unit)	Low	High	
SBP (mmHg)	\leq 90 mmHg AND change from baseline \leq -20 mmHg	≥ 180 mmHg AND change from baseline ≥ 20 mmHg	
DBP (mmHg)	≤ 50 mmHg AND change from ≤ -15 mmHg	≥ 110 mmHg AND change from baseline ≥ 15 mmHg	
Orthostatic SBP (mmHg)	\geq 20 mmHg drop with posture change from supine to standing		
Orthostatic DBP (mmHg)	≥ 10 mmHg drop with posture change from supine to standing		
Pulse rate (bpm)	≤ 50 bpm AND change from baseline ≤ -15 bpm	≥ 120 bpm AND change from baseline ≥ 15 bpm	
Orthostatic pulse rate≥ 30 bpm increase with posture change from supine to standing (bpm)			
Weight (kg)	percentage change from baseline ≤	percentage change from baseline ≥	
Temperature (°C)	-10.0% ≤ 35.0 °C	10.0 % ≥ 39.0 °C	

Note: bpm: Beats per minute. DBP: Diastolic Blood Pressure. kg: kilogram. mmHg: Millimeter of mercury. SBP: Systolic Blood Pressure

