10.5. ECG

A standard 12-Lead ECG will be recorded with the subject resting in supine for at least 5 minutes. ECGs will be performed during the Screening visit, Baseline visit, in-clinic scheduled visit or early termination visit. Results from the central ECG core lab will be included in the reporting of this study. The following ECG parameters will be reported:

- PR Interval (msec)
- RR Interval (msec)

Jazz Pharmaceuticals

Statistical Analysis Plan - Protocol JZP385-201

- QRS Interval (msec)
- QT Interval (msec)
- QT Bazett's correction (QTcB) Interval (msec) [derived]
- QT Fridericia's correction (QTcF) Interval (msec) [derived]
- Mean HR (bpm)
- Overall assessment of ECG:
 - Normal
 - o Abnormal

The following summaries will be provided for ECG data across the study:

- Observed and change from baseline by visit (for quantitative measurements)
- ECG parameters results will be listed over time

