10.5.1. ECG Abnormal Criteria

Abnormal quantitative ECG measurements will be identified in accordance with the following predefined markedly abnormal criteria:

Observed values for QT interval, QTcB interval and QTcF will be classified as follows at each time point:

- > 450 msec
- > 480 msec
- > 500 msec

Change from baseline for OT interval, OTcB interval and OTcF will be classified as follows:

- >30 msec increase from baseline
- >60 msec increase from baseline

A listing of participants meeting markedly abnormal criteria as well as a listing of participants with abnormal ECG overall assessment will also be provided based on the Safety Analysis Set.

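### The SAP has no averaging rule for triplicate ECGs or triplicate screening/baseline blood pressure and pulse; read literally, its selection rules keep one of three readings

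*SAP*

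**What the plan says.** **Collection.** The Schedule of Activities (Protocol 1.3) states: "At each time point, ECGs will be taken in triplicate at approximately 2-minute intervals". Protocol 8.3.3 repeats the triplicate design. Supine and standing blood pressure and pulse are measured three times at Screening Visit 1, Screening Visit 2 (if applicable) and Baseline, and once at later visits (Protocol 1.3 and 8.3.2).

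**Eligibility.** Exclusion criteria 7f (blood pressure), 7g (QTcF) and 20 (orthostatic change) all use the average of the three readings.

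**Analysis.** Protocol 9.4.5 gives no replicate rule. The SAP has these rules for reducing several readings to one:

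- SAP 7.2.1, Baseline: the last non-missing pre-dose value from the baseline visit, and "If a participant has repeated measurements from the baseline visit, then the last repeated non-missing value will be used".
- SAP 7.2.3, Table 5, baseline row, in a column that names vital signs and ECG: "Closest prior to dosing".
- SAP 7.2.3, window rule, which opens "If multiple assessments or measurements are recorded within a single visit window" and expressly covers repeated measurements. Scheduled visits come first, then the value nearest the target day; for same-day values, "then the non-missing observation with the earliest collection time will be included in the analysis".

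SAP 10.5 adds only that "Results from the central ECG core lab will be included in the reporting of this study". SAP 10.4, 10.4.1, 10.5 and 10.5.1 contain no averaging step, and SAP 7.6 lists no change on this point.

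**The concern.** Triplicates are collected so that they can be averaged, which removes much of the reading-to-reading noise. If the SAP is programmed as written, two of the three ECG readings are discarded at each visit. Different readings are also kept at the two ends of a change score: the last at Baseline and the first afterwards. The baseline value in the safety tables can then differ from the averaged value that made the participant eligible.

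The affected outputs are prespecified:

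- ECG and vital-sign change-from-baseline summaries;
- counts meeting the QT, QTcB and QTcF category "30 msec increase from baseline" (SAP 10.5.1 sets the threshold as above 30 msec), and the category above 60 msec;
- the change component of the Table 6 vital-sign flags, such as "180 mmHg AND change from baseline" for high systolic pressure.

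Extra noise inflates the number of participants who cross these thresholds by chance and makes a real signal harder to see against that background.

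**Working it through.** **Step 1: apply the rules as written.**

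| Measurement | Collected | Rule that applies | Value kept |
|---|---|---|---|
| ECG, Baseline | 3 | SAP 7.2.1, last value | third tracing |
| ECG, post-baseline visit | 3 | SAP 7.2.3, earliest same-day value | first tracing |
| BP and pulse, Baseline | 3 | SAP 7.2.1, last value | third reading |
| BP and pulse, Screening | 3 | SAP 7.2.3, same-day tie-break | points to first reading |
| BP and pulse, post-baseline | 1 | none needed | the single reading |

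Post-baseline orthostatic drop counts are therefore unaffected. For blood pressure and pulse, only the screening/baseline value is at issue.

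**Step 2: size for QTcF.** The documents give no SDs, so there is no plan figure to reproduce and the inputs are assumptions. Let sb be the between-visit SD (6 to 10 ms) and sw the within-visit SD between tracings (3 to 10 ms), with normal, independent components and no drug effect.

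- Single tracing at each end: SD(change) = √[2(sb² + sw²)].
- Triplicate mean at each end: SD(change) = √[2(sb² + sw²/3)].
- P(increase > 30 ms) = 1 − Φ(30/SD).

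Worked case, sb = sw = 8: single √[2(64 + 64)] = 16.00; mean √[2(64 + 21.33)] = 13.06; ratio 1.225. P = 1 − Φ(1.875) = 3.04% versus 1 − Φ(2.296) = 1.08%.

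| sb/sw (ms) | SD single | SD mean of 3 | Ratio | P(>30) single | P(>30) mean of 3 | Excess per 100 |
|---|---|---|---|---|---|---|
| 8/3 | 12.08 | 11.58 | 1.044 | 0.652% | 0.478% | 0.17 |
| 8/5 | 13.34 | 12.03 | 1.109 | 1.227% | 0.631% | 0.60 |
| 8/8 | 16.00 | 13.06 | 1.225 | 3.040% | 1.083% | 1.96 |

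Over the grid sb ∈ {6, 8, 10}, sw ∈ {3, 4, 5, 6, 8, 10}:

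- The SD ratio runs from 1.029 (10/3) to 1.401 (6/10).
- The excess runs from 0.04 per 100 participants per visit (6/3: 0.078% versus 0.034%) to 3.4 (10/10: 6.681% versus 3.310%).
- The chance of an increase above 60 ms is at most 0.135% (10/10, single tracings).

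A simulation of 2,000,000 participants, using the last baseline and first post-baseline tracing, agrees: 3.05% versus 1.08% at 8/8, and 0.66% versus 0.48% at 8/3.

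**Step 3: size for systolic pressure.** The post-baseline reading is single in both cases, so only the baseline term changes. Assume sb 6 to 10 and sw 3 to 8 mmHg.

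- One baseline reading: √[2(sb² + sw²)].
- Mean of three at baseline: √[2sb² + sw² + sw²/3].
- At 10/3: 14.77 versus 14.56, ratio 1.014.
- At 6/8: 14.14 versus 12.54, ratio 1.127.

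The SD of change is thus 1% to 13% larger with one baseline reading.

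**The case against.** **The rules may not be aimed at planned replicates.** The protocol says triplicate for planned sets and uses repeat for additional tests, and SAP 7.2.1 is qualified as a general rule. On that reading, the rules choose between separate assessments and say nothing about a triplicate set. This is possible but does not remove the problem. No exception is written for ECG or vital signs. The opening sentence of 7.2.1 (last non-missing value) and the same-day rule in 7.2.3 (any two or more observations) select one reading whatever repeated means. The window rule also lists repeated and retest measurements separately. Even on the kinder reading, the SAP has no rule for replicates.

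**The core laboratory may send one averaged value per time point.** If so, there is nothing to discard for ECG. Neither document says which it is, so this stands as a real uncertainty. Mean HR in SAP 10.5 is a listed parameter, not an averaging rule for QT, PR or QRS. The argument does not cover blood pressure and pulse, which do not come from that laboratory.

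**The size is assumed and may be negligible.** This stands. The largest figures need tracings about two minutes apart to vary as much as, or more than, readings from different visits. For vital signs, the Table 6 blood pressure and pulse flags also need an absolute threshold met by the single post-baseline reading, and no effect on those counts has been calculated.

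**Nothing inferential depends on it.** Also true: safety analyses are descriptive. Averaging for eligibility does not oblige the analysis to average, so this is an avoidable loss of precision rather than a contradiction.

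**Conclusion.** The concern holds as a minor point. The missing averaging rule is certain. Keeping one reading of three is what the stated rules give when followed literally, but it is not certain to be what is programmed, mainly because the form of the core-laboratory data is not stated.

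The size is unknown from the documents. It is small if tracings within a visit agree closely, and could reach a few chance threshold crossings per 100 participants per visit if they do not. The added noise is expected to be similar in all arms, so it should blur comparisons rather than favour an arm. Efficacy analyses, type I error and power are not affected.

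**What to change.** 1. In SAP 7.2.1 and 7.2.3, state that the mean of the available replicates at a time point is the analysis value for ECG parameters at all visits and for blood pressure and pulse at Screening and Baseline.
2. State that averaging comes before the baseline, window-selection, change and outlier rules, and that the last-value and earliest-value rules apply only to separate repeat or retest assessments.
3. In SAP 10.5, state whether core-laboratory values arrive per tracing or already averaged.

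If the sponsor intends a different reduction, the SAP should state it explicitly. The cost is two or three sentences and minor programming, with no new data.

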7.2.2. Study Day

A study day will be assigned as follows:

- The first dose of study intervention is designated as Day 1. Participants self-administer the first dose study intervention at home the day after the Baseline Visit.
- For visit days after Day 1, study day = visit date Day 1 date + 1.
- For visit days prior to Day 1, study day = visit date Day 1 date. Thus, study days for screening visit are negative numbers. There is no "Day 0".
- The end date of treatment for each subject is the subject's last dose date in the study.
- The end date of the study for each subject is defined as the date of the subject's last assessment including the safety follow-up in the study.

7.2.3. Visit Windows

All scheduled, unscheduled, and early termination assessments will be summarized by derived analysis visit per the Table 5, regardless of whether the visit was performed on-site or remotely. Visit dates will be mapped based on the scheduled Period of each visit, with adjusted analysis-defined visit windows as specified in Table 5.

Table 5 Visit Windows for Assessments or Measurements

Study Period	Scheduled Visit	Scheduled Study Day	TETRAS-ADL, TETRAS-PS, CGIs	CGIc and PGIc	QUEST, SF-36v2, ETEA	C-SSRS ^b , Clinical Laboratory ^{c, e} , Urinalysis ^e , Weight, Vital Signs, Breath Alcohol ^{d, e} , ECG, Urine Pregnancy test
Screening	Visit 1/Visit 2 ^a	-49 to -8	Any Day up to -2	na	n/a	Any Day up to -2
Baseline ^f	Baseline Visit	-1	Closest prior to dosing	na	Closest prior to dosing	Closest prior to dosing
	Week 1	7 (-1, +2)	na	na	na	2 - 14
Double-Blind	Week 4	28±3	2 - 42	2 - 42	na	15 - 42
Treatment	Week 8	56± 3	43 - 70	43 - 70	na	43 - 70
	Week 12	84± 3	71 - 98	71 – 98	2 - max	71 - max
Safety Follow-up	End of Study	98± 3	na	na	2 - max	2 – max ^f

^a Screening Visit 2 is only for participants who need to wash out of any medications that impact tremor (e.g., anti-tremor medications) prior to Baseline;

^b At screening visit 1, C-SSRS screening/baseline version, at screening visit 2, C-SSRS since last visit version;

^c Clinical laboratory includes hematology and chemistry labs;

^dBreath Alcohol is not collected at W1;

^e Not collected at Safety Follow-up.

^f For participants who randomized without taking the study intervention, the Baseline Visit or latest Screening Visit (if Baseline Visit is not available) will be mapped.

If multiple assessments or measurements are recorded within a single visit window (including scheduled, unscheduled, repeated, and retest assessments or measurements as well as early discontinuation data), the following rules will be applied to determine the result from which assessment will be used for the summaries for that analysis visit.

- The priority will always be given to the scheduled visit within the corresponding visit window (e.g., scheduled W4 visit corresponds to Week 4 visit window) regardless of the relative distance to the scheduled Visit Day.
- If there are 2 or more observations within the same visit window, then the non-missing one closest to the scheduled Visit Day will be used in the analysis.
- If 2 or more observations are equidistant from the scheduled Visit Day, then the non-missing observation with the earliest collection date will be used in the analysis.
- If 2 or more observations are collected on the same day and this day is the closest to the scheduled Visit Day, then the non-missing observation with the earliest collection time will be included in the analysis.

Screening Visit 1 and Visit 2 will be treated as two visits. Observations from the two visits will be summarized separately, as applicable.

If a visit window does not contain any observations, then the data will remain missing for the analysis visit.

Listings will include scheduled, unscheduled, repeated, retest, and early termination data per nominal visits.

